**Drug rash:**

A benign maculopapular exanthema consistent with a delayed type drug rash has been seen in 3 subjects taking multiple doses of BCX7353 to date. In Studies BCX7353-101 and BCX7353-102, a total population of BCX7353 exposed subjects who have received at least 7 days of BCX7353 doses is 68, equating to an incidence rate of 4.4%. In all cases, symptoms were observed or reported approximately 2 days after daily BCX7353 dosing ended: one subject who completed 500 mg QD BCX7353 x 7 days (Study BCX7353-101), one subject of Japanese heritage who completed 250 mg QD BCX7353 x 7 days (Study BCX7353-101), and one subject who recently completed 9 days of BCX7353 350 mg QD (Study BCX7353-102). In all cases, no systemic or constitutional symptoms, no organ involvement, no desquamation or mucosal involvement was observed, no clinically significant laboratory abnormalities were present and the rash rapidly resolved. Two subjects received an oral antihistamine and 1 subject received oral and topical steroids.

Hypersensitivity is a risk with any drug. In all three cases, the rashes have been limited and resolved quickly. Subjects should report any rashes, pruritus, or skin changes. Evaluation of any suspected drug-induced rash will be required with high resolution photography and clinical laboratory assessments in order to better define this risk; skin biopsy of a fresh lesion should be obtained for histopathologic examination, where possible. In addition, human leukocyte antigen (HLA) typing of all future enrolled subjects in multiple dose trials is being undertaken to understand whether any specific HLA genotypes play a role in the development of cutaneous hypersensitivity and could be used to identify patients at higher risk.

**5.4.5. Benefits of Trial Participation**

Study subjects will receive regular medical care for the duration of the study. Subjects may experience a reduction in the number of attacks while receiving active study drug for 28 days, although subjects will not know if they are receiving BCX7353 or placebo.

Participation in this study will not exclude study subjects from being able to participate in longer term open-label studies of BCX7353, if further development of the drug is warranted. The development of BCX7353 may be of benefit to the wider community/patients with HAE.

**5.4.6. Overall Benefit-Risk Assessment**

The risks seen to date in both preclinical and clinical studies at the study doses were primarily mild, monitorable, and reversible. Even findings in animals such as PLD that are not directly monitorable will be followed by robust assessment of organ health and function. Although there may be no direct benefit to any individual subject, the information obtained from this trial will support the development of BCX7353 for HAE, a serious, debilitating and potentially life threatening disease.

The overall risk benefit balance is therefore considered to be acceptable.

## **6. TRIAL OBJECTIVES AND PURPOSE**

### **6.1. Objectives**

The primary objective of this study is as follows:

- To evaluate the efficacy of once-daily prophylactic BCX7353 at up to 5 dose levels, as measured by the number of attacks of HAE observed in patients with HAE enrolled in each treatment group

The secondary objectives of this study are as follows:

- To evaluate the safety and tolerability of BCX7353 over 28 days in subjects with HAE
- To describe the PK profile of daily BCX7353 in subjects with HAE
- To characterize the anticipated PD effects of BCX7353 in subjects with HAE
- To characterize the dose-response relationship of BCX7353 in subjects with HAE
- To evaluate effects of BCX7353 on quality of life

## 7. INVESTIGATIONAL PLAN

### 7.1. Overall Study Design and Plan: Description

This is a Phase 2, randomized, double-blind, placebo-controlled parallel-group, dose-response study to evaluate the safety, tolerability, PK, PD, and efficacy of BCX7353 in subjects with HAE. HAE patients with a documented recent history of frequent angioedema attacks who have provided written informed consent will be evaluated for participation in this study at a screening visit.

Up to 36 subjects with HAE are planned to be enrolled in Part 1 of the study and will be randomized 1:1 (placebo: active) to receive one of the following treatments:

- Part 1, Treatment Group 1: placebo QD orally for 28 days
- Part 1, Treatment Group 2: 350 mg BCX7353 QD orally for 28 days

After 24 subjects have completed through the Day 28 dose, there will be an administrative interim analysis of the accrued efficacy data by the Sponsor. If it is desired to more fully characterize the treatment effect of BCX7353 relative to placebo or to verify assumptions made for sizing this proof-of-concept study, additional subjects will be enrolled to complete Part 1 (up to 36). Enrollment into Part 1 will continue until either a decision is made to halt enrollment in favor of opening Part 2 or enrollment reaches 36 subjects in Part 1. Additionally, upon completion of Part 1 (36 subjects dosed), enrollment into Part 2 of the study may immediately commence.

In Part 2, approximately 14 subjects who meet all eligibility criteria are planned to be randomized in a 1:3:3 (placebo:active:active) ratio into 1 of the following 3 treatment groups:

- Part 2, Treatment Group 1: placebo QD orally for 28 days
- Part 2, Treatment Group 2: 125 mg BCX7353 QD orally for 28 days
- Part 2, Treatment Group 3: 250 mg BCX7353 QD orally for 28 days

If tolerability issues prevent full enrollment of Part 1 as described or study drug is poorly tolerated due to gastrointestinal effects, future subjects randomized to active study drug in Part 1 may receive 250 mg orally once daily for 28 days. In this case, any dose level changes warranted for Part 2 will be instituted via protocol amendment.

Following completion of enrolment in Part 2, Part 3 of the study may be initiated:

In Part 3, approximately 20 subjects who meet all eligibility criteria are planned to be randomized in a 1:3:3:3 (placebo:active:active:active) ratio into 1 of the following 4 treatment groups:

- Part 3, Treatment Group 1: placebo QD orally for 28 days
- Part 3, Treatment Group 2: 125 mg BCX7353 QD orally for 28 days
- Part 3, Treatment Group 3: 250 mg BCX7353 QD orally for 28 days
- Part 3, Treatment Group 4: 62.5 mg BCX7353 QD orally for 28 days

Following completion of enrollment in Part 3, Part 4 of the study may be initiated in order to more fully define the dose-response relationship. The decision to enroll Part 4, including the doses selected for study, will be based on results through Part 3 of the study.

Should the 62.5 mg and 125 mg BCX7353 dose groups in Part 3 be less efficacious than higher doses of BCX7353 and Part 4 is initiated, approximately 14 subjects in Part 4 will be randomized in a 1:6 ratio into 1 of the following 2 treatment groups:

[figure not shown]
- Part 4, Treatment Group 1: placebo QD orally for 28 days (n=2)
- Part 4, Treatment Group 2: 175 mg BCX7353 QD orally for 28 days (n=12)

Alternatively, should the 62.5 mg BCX7353 dose group not be shown to be less efficacious after analysis of Part 3 data and Part 4 is initiated, approximately 20 subjects in Part 4 will be randomized in a 1:6:3 (placebo:active:active) ratio into 1 of the following 3 treatment groups as follows:

- Part 4, Treatment Group 1: placebo QD orally for 28 days (n = 2)
- Part 4, Treatment Group 2: 175 mg BCX7353 QD orally for 28 days (n = 12)
- Part 4, Treatment Group 3: 62.5 mg BCX7353 QD orally for 28 days (n = 6)

The overall study design is presented in [Figure 3](#); [Figure 4](#) depicts the schema for conduct of each study part.

**Figure 3: Study BCX7353-203 Study Design**

Following an up to 21-day screening period, eligible subjects, who have had entry criteria confirmed by the Sponsor, will be dosed on Day 1. Subsequent study visits will be held on Days 7, 14, 21 and 29. At the Day 14 visit, subjects will also have serial blood samples drawn immediately prior to and after the dose, including a visit on Day 15 for collection of a 24-hour postdose PK sample. A follow-up visit will be performed on Day 44.

[figure not shown]
Subjects will record the occurrence and details of all angioedema attacks at least once daily beginning from the date of screening until the follow-up visit. On Days 1 through 28, subjects will also record the time of day the study drug (BCX7353 or placebo) was taken and the number of capsules of study drug taken at each dose. Subject-reported study drug administration and HAE attacks will be captured in a diary.

During the study, each subject will continue to use their prescribed acute attack medication to treat any attacks, under the medical management plan advised by their physician. All participants must have access to effective, approved treatments for attacks of angioedema as part of their routine medical care.

Subject will only participate in one part of the study.

All subjects who successfully complete treatment in the study will be offered the opportunity to participate in a future long-term study of BCX7353 where locally approved, provided that development of BCX7353 continues.

**Figure 4: Study Schema—Parts 1, 2, 3 and 4**

\*A 62.5 mg dose will only be included in Part 4 if the data from Part 3 does not exclude efficacy at this dose level

## 7.2. Endpoints

### 7.2.1. Primary Efficacy Endpoint

The primary efficacy endpoint is the number of confirmed HAE attacks during the treatment period in the Full Analysis Set (FAS) population. The number of HAE attacks will be analyzed by treatment group using appropriate descriptive statistics as follows: weekly attack rate, counts

of attacks, proportion of subjects with no attacks, and number of attack-free days. The relative change in attack rate from placebo will also be calculated for each active arm. The FAS includes all randomized subjects who receive at least 1 dose of study drug and have post baseline HAE attack data.

To ensure that consistent, objective assessments are used in accepting subject-reported attack data, a panel of expert physicians in the treatment of HAE patients will adjudicate all subject-reported attacks prior to their inclusion in primary efficacy analyses. The adjudication will be based upon all data provided by the subjects in their study diaries that document reported HAE attacks. A separate charter will describe membership, roles, and processes to be followed by the adjudication panel.

### **7.2.2. Secondary Efficacy Endpoints**

Secondary endpoints will include the following:

- Number of attacks requiring attack medication
- Duration of attacks
- Severity of attacks
- Attack onset relative to the time of last dose of study drug
- Discontinuations due to lack of efficacy
- Symptoms and anatomical locations of attacks
- Number of emergency room visits and/or hospitalizations

### **7.2.3. Safety Endpoints**

Safety endpoints will include the number and proportion of subjects: who discontinue due to a treatment-emergent AE; who experience a treatment-emergent serious adverse event (SAE); who experience a Grade 3 or 4 treatment-emergent AE; and who experience treatment emergent Grade 3 or 4 laboratory abnormalities.

### **7.2.4. Other Secondary Endpoints**

Other secondary endpoints will include quality of life scales, as measured by the Angioedema Quality of life (AE-QoL) (Weller, Groffik et al. 2012) and Depression, Anxiety, Stress Scales (DASS) (Crawford and Henry 2013). In addition, serial PK parameters and PD endpoints will be reported.

## 8. SELECTION AND WITHDRAWAL OF SUBJECTS

### 8.1. Number of Subjects

Approximately 58 to 90 subjects are planned to be randomized and enrolled in this study: up to 36 subjects in Part 1 (350 mg or placebo) and approximately 14 subjects in Part 2, approximately 20 subjects in Part 3, and approximately 14 or 20 subjects in Part 4 (number predicated on results from 62.5 mg BCX7353 Treatment Group in Part 3). In the event that the active study drug dose is modified in Part 1 to 250 mg, up to 36 additional subjects may be enrolled into Part 1 (see Section 9.5.2) for a total of 126 subjects enrolled in this study (78 to 84 subjects receiving active study drug).

Subjects who withdraw from the study may be replaced at the Sponsor's discretion. Any subject that has withdrawn from the study as a result of a treatment-emergent AE (regardless of severity or causality) may not be replaced.

The following inclusion and exclusion criteria will be used to screen subjects for the study.

### 8.2. Subject Selection

#### 8.2.1. Inclusion Criteria

Subjects must meet all of the following inclusion criteria to be eligible for participation in this study:

1. Able to provide written, informed consent
2. Males and non-pregnant, non-lactating females age 18 to 70 years
3. A clinical diagnosis of hereditary angioedema Type 1 or Type 2 as documented at any time in the medical records or at the screening visit by a low C1 INH functional level (Type 2) or a low C1 INH antigenic level (Type 1)
4. A documented HAE attack rate of at least 2 HAE attacks per month for 3 consecutive months (defined as 93 days) within the 6 months prior to the screening visit as documented in acceptable source records.

Source records of historical HAE attacks must exist (for all subjects) that permit a qualifying HAE attack rate to be calculated. Any of the following will be acceptable source records of HAE attacks: clinic notes with a numerical rate of attacks, acute attack medicine administration records, or a historically-completed subject record of attacks. This record should indicate the dates of attacks, at a minimum.

***NOTE: under no circumstances can the attack criterion threshold for enrollment be disclosed to any subject***

5. Access to and ability to use 1 or more acute medications approved by the relevant competent authority for the treatment of attacks of HAE (icatibant, plasma-derived C1 INH or recombinant C1 INH).

6. Female participants must meet at least 1 of the following requirements:
- a. Be a woman of childbearing potential (defined as a nonmenopausal female who has not had a hysterectomy, bilateral oophorectomy, or documented ovarian failure) who agrees to use at least an acceptable effective contraceptive method during the study and for a duration of 30 days after last dose of study drug. One or more of the following methods are acceptable:
    - surgical sterilization (ie, bilateral tubal occlusion or vasectomy of male partner)
    - placement of an intrauterine device (IUD) or intrauterine system (IUS) (implanted any time prior to or during screening)
    - progesterone-only (implantable or injectable only) hormonal contraception associated with inhibition of ovulation initiated at least 60 days prior to the screening visit
    - male or female condom with or without spermicide
    - use of an occlusive cap [diaphragm, or cervical/vault caps] with spermicide (foam/gel/film/cream/suppository)

Female subjects who report being postmenopausal for  $\leq 2$  years and have a screening follicle-stimulating hormone (FSH)  $\leq 40$  mIU/mL must agree to use at least an acceptable effective contraceptive method and (as proposed above) during study and for 30 days after the last dose of study drug.
  - b. Be a woman of nonchildbearing potential (defined as postmenopausal for  $> 2$  years or having a screening FSH  $> 40$  mIU/mL if postmenopausal  $\leq 2$  years or have had a hysterectomy, bilateral oophorectomy, or documented ovarian failure).
  - c. Be a woman declaring herself as either sexually abstinent or exclusively having female sexual partners. Abstinence in this study is defined as "true abstinence: when this is in line with the preferred and usual lifestyle of the subject."
7. Male subjects must comply with the following requirements during the study and for a duration of 90 days after last dose of study drug:
- a. Subjects with female partners of childbearing potential (defined as postmenopausal  $\leq 2$  years or a nonmenopausal female who has not had a hysterectomy, bilateral oophorectomy, or documented ovarian failure) must agree to utilize at least 1 acceptably effective contraceptive method. At least 1 or more of the following methods are acceptable:
    - surgical sterilization (i.e., vasectomy or bilateral tubal occlusion of a female partner)
    - placement of an IUD or IUS
    - any form of hormonal contraception (oral, implantable, injectable, intravaginal, or transdermal)
    - use of a condom with or without spermicidal foam/gel/film/cream/suppository

- partner's use of an occlusive cap [diaphragm, or cervical/vault caps] with spermicidal (foam/gel/film/cream/suppository)
  - b. Male subjects who declare themselves as sexually abstinent are acceptable for the purposes of this study. Abstinence in this study is defined as "true abstinence: when this is in line with the preferred and usual lifestyle of the subject."
  - c. Male subjects who exclusively have male partners must consent to using a condom during intercourse throughout the duration of the study.
  - d. Must abstain from sperm donation during the study and for a period of 90 days after last dose of study drug.
8. Any concomitant medication not stated as prohibited must be anticipated to be continued through the entire study and be of a stable dose and regimen for the duration of the entire study.
  9. In the opinion of the Investigator, the subject is expected to adequately comply with all required study procedures for the duration of the study. The subject must demonstrate adequate compliance with all study procedures required from the screening visit through randomization, including diary recording of HAE attacks beginning at the screening visit.

### 8.2.2. Exclusion Criteria

Subjects must meet none of the numbered exclusion criteria below to be eligible for participation in this study. Medications prohibited for use during the study are addressed in Section 9.7.1.

1. Any clinically significant medical or psychiatric condition or medical history that, in the opinion of the Investigator or Sponsor, would interfere with the subject's ability to participate in the study or increases the risk to the subject of participating in the study.
2. Dementia, altered mental status, or any psychiatric condition, or stay in an institution further to an official or court order that would prohibit the understanding or rendering of informed consent or participation in the study.
3. Use of C1 INH, androgens, or tranexamic acid for prophylaxis of HAE attacks within the 7 days prior to the screening visit or initiation during the study. Androgen use is not permitted at any time during the study. Use of a C1 INH therapy for treatment of attacks is not excluded at any time.
4. Clinically significant abnormal ECG at the screening visit. This includes, but is not limited to, a QTcF > 470 msec, a PR > 220 msec, or ventricular and/or atrial premature contractions that are more frequent than occasional, and/or as couplets or higher in grouping.
5. Any clinically significant history of angina, myocardial infarction, syncope, clinically significant cardiac arrhythmias, left ventricular hypertrophy, cardiomyopathy, or any other cardiovascular abnormality.
6. Known family history of sudden death from causes other than HAE.
7. History of or current implanted defibrillator or pacemaker.

8. Any abnormal laboratory or urinalysis parameter at screening that, in the opinion of the Investigator, is clinically significant and relevant for this study. A calculated  $CL_{cr}$  (see Section 11.1.6) of  $\leq 60$  mL/min or AST or ALT value  $\geq 2$  times the upper limit of the normal reference range value obtained during screening is exclusionary.
9. Suspected C1INH resistance in the opinion of the Investigator and Sponsor.
10. History of alcohol or drug abuse within the previous year prior to the screening visit, or current evidence of substance dependence or abuse (self-reported alcoholic intake  $> 3$  drinks/day).
11. Positive serology for human immunodeficiency virus (HIV) or active infection with hepatitis B virus (HBV) or hepatitis C virus (HCV).
12. Pregnant, planning to become pregnant within 30 days of the study, or nursing.
13. Positive drugs of abuse screen (unless as used as medical treatment, e.g., with a prescription).
14. History of severe hypersensitivity to any medicinal product.

### **8.3. Subject Withdrawal Criteria**

#### **8.3.1. Subject Discontinuation from Study**

Participation in the study is strictly voluntary. The only reason permitted for withdrawal from the study is a subject's withdrawal of consent to contribute additional study information. A subject who withdraws consent prior to study completion will be requested to attend an early termination visit to complete all end-of-study evaluations. In all cases, the reason for withdrawal must be recorded in the subject's medical records (source documents) and also in the electronic case report form (eCRF). If the reason for subject withdrawal is not known, the subject must be contacted to establish whether the reason was an AE, and if so, this must be reported in accordance with the procedures outlined in Section 12.

Once subjects have discontinued the study, the Sponsor will no longer provide treatment through the study. Following withdrawal from the study, a subject will be able to receive further treatment as recommended by their treating physician and according to the accepted standard of care.

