#### **8.3.2. Subject Discontinuation from Study Drug**

A subject may be withdrawn from study drug for any of the following bulleted reasons, which will be recorded in the source documents and eCRF. In all cases, subjects who discontinue study drug will be requested to complete all regularly scheduled visits and procedures outlined in Table 3.

- Emergence of any laboratory abnormality or adverse event that in the judgment of the Investigator compromises the ability to continue study-specific procedures or is considered not to be in the subject's best interest
- Intercurrent illness that would, in the judgment of the Investigator, affect assessments of clinical status to a significant degree

- Subject noncompliance with study drug or to the protocol
- Discontinuation at the request of the Sponsor, competent authorities in the Member State(s) concerned, or the institutional review board (IRB)/independent ethics committee (IEC)

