**Table 3: Schedule of Assessments for Study BCX7353-203**

Assessment	Screening	Baseline Day 1 u							Follow-up (or Early Term [ET])
	Day -21 to -1	Day 1 Pre- Dose	Day 1 Post- dose	Day 7 ± 1 days	Day 14 ± 2 days	Day 15 t Pre-dose	Day 21 ± 1 days	Day 29 + 1 day	Day 44 + 7 days
Informed consent a	X								
Clinic visit b	X	X		X	X	X	X	X	X
Inclusion/ Exclusion criteria & prohibited medications	X	X							
Medical history	X	X							
HAE medical and medication history	X								
Height/Weight/BMI	X	X d			X d			X d	X d
Drugs of abuse screen e	X								
HIV/HCV/ HBV serology	X								
C1 INH antigenic and/or functional level f	X	X						X	
Physical examination g	X	X g			X g			X g	X g
12-lead ECG h	X	X			X			X	X
Vital signs i	X	X			X			X	X
Pregnancy test j	X	X			X			X	X
FSH k	X								
D L CO	X							X l	
Chemistry, hematology and coagulation laboratory evaluations c	X	X			X			X	X
Liver Function Test e				X			X		
Troponin I & Troponin T		X			X			X	X

Assessment	Screening	Baseline Day 1 u							Follow-up (or Early Term [ET])
	Day -21 to -1	Day 1 Pre- Dose	Day 1 Post- dose	Day 7 ± 1 days	Day 14 ± 2 days	Day 15 t Pre-dose	Day 21 ± 1 days	Day 29 + 1 day	Day 44 + 7 days
C3		X							
HLA typing m		X							
Optional sample for possible exploratory pharmacogenomic testing v		X							
NGAL		X			X			X	X
CK-MB		X			X			X	X
Urinalysis c	X	X			X			X	X
Attack frequency confirmation	X								
Sponsor approval and randomization n	X								
HAE attack and dosing diary instruction/review/collection o	X	X	X	X	X	X	X	X	X
Diary completion p									
AE-QoL and DASS		X			X x			X	
Plasma for PK analysis q		X			X t	X t		X	
Plasma for kallikrein inhibition q		X			X t	X t		X	
Plasma for additional PD analysis r		X			X			X	
Concomitant medications	X	X	X	X	X	X	X	X	X
AE assessment	X	X	X	X	X	X	X	X	X
study drug accountability/dispensing			X		X w			X	X (ET)
study drug dosing s									

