- t Subjects unable to undergo the serial PK blood draw on study Day 14 will only have a predose or trough blood sample drawn; a steady-state serial PK blood collection will then be obtained on Day 28 with a 24-hour blood draw conducted at the scheduled visit on Day 29. In the event the serial PK is not conducted on Day 14, the Day 15 visit is not required.
- u If the site is unable to conduct all procedures for an individual subject at Baseline on Day 1 because of logistical reasons, refer to [Section 10.3.2](#) for procedures that may be conducted on Day -1.

- v A blood sample for possible exploratory pharmacogenomic testing will be drawn at the Baseline/Day 1 sample only if consent is obtained for this optional testing; if a blood sample is not obtained at Baseline, the sample may be drawn at any time during the study following consent obtained from the subject.
- w Study drug may be dispensed to the subject on Day 15 after in-clinic dosing in lieu of dispensing on Day 14 if preferred.
- x The AE-QoL questionnaire will not be administered at the Day 14 visit.

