### **10.3.8. Follow-up/Early Termination Visits**

Subjects who discontinue treatment early must continue to complete all regularly scheduled visits and procedures as outlined in [Table 3](#). As indicated in [Section 8.3.1](#), the only reason for withdrawal from the study is a subject's withdrawal of consent. A subject who withdraws consent prior to study completion will be requested to attend a termination visit to complete all end-of-study evaluations.

For all subjects who complete treatment the follow-up visit should be conducted on follow-up Day 44 (+ 7 days). Assessments to be performed at this visit are outlined in [Table 3](#) and described in [Section 11](#). In the event that there are clinically significant findings from safety assessments that are ongoing at follow-up Day 44, the subject will be followed at additional study visits until the findings are resolved or stabilized at a new baseline.

The following assessments will be performed at the follow-up or early termination visit:

- Subject weight
- Targeted physical examination
- Vital signs (blood pressure and heart rate)
- 12-lead ECG
- Review of concomitant medications and AEs
- Blood collection for clinical chemistry, hematology and coagulation
- Urine collection for urinalysis and urine pregnancy test for female subjects of child-bearing potential
- Blood collection for Troponin I and Troponin T, NGAL, and CK-MB
- Study drug accountability (for subjects who discontinued treatment early)
- Review and collection of the attack diaries

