## **11.2. Subject-Completed Assessments**

### **11.2.1. Quality of Life Questionnaires**

To assess quality of life, the AE-QoL and DASS questionnaires will be administered once at Baseline, Day 14 (DASS only) and at Day 29.

For all subject-completed forms, clinic staff should ensure the subject reads the instructions and completes the questionnaires in full prior to filing in the source documentation.

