## **10. DATA HANDLING CONVENTIONS**

### **10.1. Missing Data and Data Handling Rules**

For subjects who prematurely discontinue the study, all available data will be included in the analyses. The planned safety and efficacy analyses will be based on the reported data. Sensitivity analyses on the primary efficacy endpoint will consider imputation methods; details are discussed in section 12.1.3.

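### The early termination visit omits AE-QoL and DASS, so a subject who withdraws consent before Day 29 has no post-baseline AE-QoL value and drops out of that analysis

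*Protocol*

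**What the plan says.** Leaving the study and stopping study drug are separate events in this protocol.

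- **Leaving the study.** Protocol 8.3.1: "The only reason permitted for withdrawal from the study is a subject's withdrawal of consent to contribute additional study information". It continues: "A subject who withdraws consent prior to study completion will be requested to attend an early termination visit to complete all end-of-study evaluations". The evaluations meant are not defined there.
- **Stopping drug.** Protocol 8.3.2: "In all cases, subjects who discontinue study drug will be requested to complete all regularly scheduled visits and procedures outlined in Table 3". Section 10.3.8 repeats this as an obligation.
- **Content of the early termination visit.** Table 3 combines it with the Day 44 follow-up in one column. The AE-QoL and DASS row is marked on Day 1, Day 14 and Day 29 and is blank in that column. Section 10.3.8 introduces its list with "The following assessments will be performed at the follow-up or early termination visit" and names neither questionnaire.
- **Questionnaire times.** Protocol 11.2.1: "the AE-QoL and DASS questionnaires will be administered once at Baseline, Day 14 (DASS only) and at Day 29". A footnote to Table 3 confirms: "The AE-QoL questionnaire will not be administered at the Day 14 visit".
- **Analysis.** SAP 12.1.4.1 analyses change from baseline in AE-QoL by ANCOVA, with Day 29 as the only post-baseline visit. SAP 12.1.4.2 uses a mixed-model ANCOVA for DASS and also names only baseline and Day 29 for display. SAP 10.4 sets change to missing when the post-dose value is missing. On incomplete data, SAP 10.1 says "The planned safety and efficacy analyses will be based on the reported data", and it considers imputation for the primary endpoint only.

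**The concern.** For a subject who leaves before Day 29, the early termination visit is the last chance to obtain an end-of-treatment quality-of-life score. The visit is planned and the subject is in the clinic, but the schedule does not ask for the questionnaires. A score not collected then cannot be recovered later.

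Effect on quality of life is a stated secondary objective, and SAP 12.1.4.1 plans confidence intervals and p-values for each dose against placebo. The protocol also foresees that some withdrawals will be linked to adverse events: 8.3.1 has sites find out whether an unexplained withdrawal was due to one, and 8.1 restricts replacement of subjects withdrawn for one. If withdrawal is related to how subjects feel, an analysis of completers estimates something other than the effect in all treated subjects.

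**Working it through.** The plan states no figure on this point, so there is none to reproduce. The check has two parts.

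**1. What is missing, and for whom**

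| Subject | AE-QoL after baseline | DASS after baseline |
|---|---|---|
| Stops drug, stays in study | Day 29 planned | Day 14 and Day 29 planned |
| Withdraws consent before Day 14 | none | none |
| Withdraws consent after Day 14, before Day 29 | none | Day 14 only |

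For AE-QoL, each subject in the last two rows has a missing change score (SAP 10.4) and no imputation (SAP 10.1). No SAP rule assigns an early-termination value to a visit; SAP 10.7 works from nominal times. The ANCOVA is therefore in effect complete-case. For DASS this is not established, because the SAP does not say whether Day 14 enters the mixed model.

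**2. Size of a possible shift**

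Let *n* be the arm size, *k* the number lost, and *gap* the mean change in withdrawers minus that in completers. AE-QoL runs from 0 (best) to 100 (worst), so a positive gap means withdrawers do worse. For the unadjusted arm mean:

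completer mean − full-arm mean = −(*k*/*n*) × gap

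Arm sizes:
- 6: 62.5 mg in Part 3 (20 × 3/10); also 250 mg at the interim.
- 7: 125 mg at the interim.
- 12: 125 mg or 250 mg pooled over Parts 2 and 3 (14 × 3/7 + 20 × 3/10 = 6 + 6).
- 18: 350 mg.

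The gap is an assumption.

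| Lost | Share of arm | Shift, gap 10 | Shift, gap 20 |
|---|---|---|---|
| 1 of 6 | 16.7% | −1.67 | −3.33 |
| 1 of 7 | 14.3% | −1.43 | −2.86 |
| 1 of 12 | 8.3% | −0.83 | −1.67 |
| 1 of 18 | 5.6% | −0.56 | −1.11 |

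The sign reverses if withdrawers do better, and the shift is zero if the gap is zero.

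Between arms, the bias (active minus placebo) is the difference of the two shifts. Three illustrations with invented withdrawal counts:
- 3 of 18 against 0 of 20, gap 10: −(3/18) × 10 = −1.67, in favour of active.
- 3 of 18 in both arms, gap 10 in both: 0.
- 3 of 18 with gap 5 against 1 of 20 with gap 20: −0.83 + 1.00 = +0.17, against active.

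More withdrawals in an arm therefore do not settle the direction of the bias.

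**The case against.** The strongest reply is that the protocol already keeps most of the relevant subjects. Anyone who stops drug for gastrointestinal symptoms or another adverse event is asked to complete the full schedule, including Day 29. The three adverse-event discontinuations reported at the interim, all at 350 mg (Protocol 5.3.3.1), were from study drug, and the interim summary mentions no consent withdrawals. This stands, and it limits the gap to consent withdrawals before Day 29.

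A reader might infer that the analysis flatters whichever dose is less well tolerated. The documents do not support that. It needs withdrawers to score worse than completers and to be more frequent at that dose, and neither is shown. The arm with the clearest tolerability signal, 350 mg, is also the largest active arm at the interim, so each loss there weighs least.

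The fix also has limits. These subjects have withdrawn consent to give further information and are only asked to attend. Their scores would be off-schedule, and because DASS asks about the past week, they may partly reflect days off drug. This reduces the yield but does not argue against collecting scores from those who do attend.

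Finally, quality of life is one of the other secondary endpoints (Protocol 7.2.4) in a Phase 2 study with no formal hypotheses and no multiplicity adjustment. That argues for a low priority. It does not justify leaving the gap open.

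Nothing comparable is shown for the PK and kallikrein samples. Serial sampling is on Day 14, or Day 28 as fallback, and the Day 29 sample is timed to about 24 hours after the last dose, which an unscheduled visit cannot guarantee.

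**Conclusion.** The gap is real: Table 3 and 10.3.8 agree in leaving both questionnaires out of the early termination visit, and the SAP has no missing-data method for quality of life. A subject who withdraws consent before Day 29 contributes nothing to the AE-QoL analysis and has no Day 29 DASS.

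The consequence is a possible bias in the AE-QoL comparison, of unknown direction and size. Under an assumed gap of 10 to 20 points, one loss shifts an arm mean by 1.7 to 3.3 points in an arm of 6 and by 0.6 to 1.1 points in an arm of 18. These figures depend on the assumed gap and on a withdrawal occurring at all. No primary, safety or power result is affected. This is a cheap improvement of limited impact.

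**What to change.** **Protocol.** In Table 3 and 10.3.8, mark AE-QoL and DASS at the early termination visit when it takes place before the Day 29 assessments have been done. Table 3 already has one entry specific to early termination, for drug accountability, so the format exists. In 8.3.1, make the end-of-study evaluations refer to that set. A C1 INH function sample at the same visit is optional; its only scheduled post-dose sample is also Day 29. Align the copy of the schedule in SAP Table 1.

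**SAP 12.1.4.1 and 12.1.4.2.** Keep Day 29 as the main analysis. Add a sensitivity analysis that takes the early-termination value as the end-of-treatment score. Report the number of missing quality-of-life scores by arm, with reasons. State whether the Day 14 DASS enters the mixed model.

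**Cost.** A few table entries, a short addition to the SAP, and a few minutes of questionnaires at a visit already planned. The added values will be off-schedule, may partly reflect off-drug days, and will come only from withdrawers who agree to attend; any bias from the others remains. Sample size, power and alpha do not change.
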